Protocol Title: Outcome of body composition assessment in patients with severe obesity undergoing metabolic surgery

Short Title: Body Composition Outcomes in MS patients (BCOMS)

PI Name: [name] [name]

Sub-Investigator's Name(s):

[name]
[name]
[name]
[name]
[name], MSN, FNP-C
[name] [name]
[name], RND

Protocol Version Date: 3/20/2026

IRB Review History

Revision 1.7

Objectives

The objective of this project is to generate pilot data substantiating our hypothesis that advanced body composition measurement tools will provide more accurate and clinically relevant data on the outcomes of metabolic surgery (MS) in patients with severe obesity compared to traditional methods.

To achieve this objective, we propose the following aims:

Aim 1: Evaluate the effectiveness of different body composition measurement tools in assessing outcomes in patients with severe obesity undergoing MS. We hypothesize that advanced body composition measurement tools will provide more accurate and clinically relevant data on the outcomes of MS in patients with severe obesity compared to traditional methods.

Aim 2: Assess the changes in body composition and muscle strength following MS. We hypothesize that 6 months post MS, patients will experience a reduction in muscle strength, along with a more significant decrease in fat mass compared to muscle mass.

Aim 3: Compare body compositions changes between SG and RYGB patients. We hypothesize that RYGB patients will experience greater reductions in subcutaneous, visceral, and total fat compared to SG patients after 6 months.

Background

Metabolic surgery (MS) is the most effective long term obesity treatment in patients with severe obesity¹⁻⁴. The prevalence of obesity among US adults is 40.3% and the prevalence of severe obesity is 9.4% (2021-2023)⁵⁻⁶. Despite the prevalence and severity of obesity, there is a significant knowledge gap regarding the most effective tools for assessing body composition in this population⁴. Traditional methods such as BMI and waist circumference may not accurately reflect changes in body composition, particularly

in patients with higher BMI. Current literature on body composition measurements in patients with severe obesity undergoing bariatric surgery is limited.

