This is a single-center, non-randomized clinical trial to evaluate body composition outcomes in participants undergoing MS. The pilot study will recruit 20 participants with severe obesity undergoing MS.

We will attempt to recruit participants of all racial and ethnic backgrounds. The majority of our participants live in the area surrounding Baton Rouge.

Equitable Selection of Participants: Individuals of either sex or individuals from any social class, are eligible to participate in the study if they are deemed acceptable candidates based on inclusion/exclusion criteria.

Recruitment Methods

The eligible and interested participants in the current study will be recruited at the Metamor Institute, PBRC. Participants should be scheduled for metabolic surgery prior to enrollment.

Once prospective participants are identified, the clinical research coordinator and/or study investigator will contact the potential participant and determine if the participant has any questions regarding the study and/or consent form. The participant's medical history will be reviewed as well as determination of the subject meeting inclusion and exclusion criteria.

After determination of eligibility by the study staff, the participant will be scheduled for a study visit. An email copy or paper copy of the consent form will be provided to the subject that will subsequently be signed upon arrival on the first study day.

Upon arrival on the study day, the informed consent document will be signed, vital signs and body weight/body mass index confirmed. Pregnancy testing will be performed on women of childbearing potential per current PBRC policy.

Duration of Study Participation

Each participant will complete a single study visit that will take approximately 5 hours.

There will be a total of 2 study visits. The first visit will be before MS and the second visit will be 6 months after surgery.

Procedures	Visit #1 (before surgery)	Visit #2 (6 months after surgery)
Informed Consent	X	
Blood taking and urine testing (pregnancy test in women of childbearing age)	X	X
Vital sign	X	X
Drink Deuterium then Bromide dilutions	X	X
Dual-Energy X-ray Absorptiometry (DXA)	X	X
BodPod (Densitometry/ Air Displacement Plethysmography)	X	X
Complete diet, eating habit and physical activity questionnaires	X	X
3D Optical imaging	X	X
Waist Circumferences measurement	X	X
Six-minute Walk	X	X
Leg strength and endurance	X	X
Collect blood samples at 4 hours post (Deuterium then Bromide dilutions)	X	X

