Q1 July-September 2025	
 a. Complete the final study protocol b. Submit the protocol & any other related documents for review to the Ethics Board/IRB. c. Receive Ethics Board/IRB protocol approval d. Participant recruitment
Q2 October-December 2025	
 a. Training and calibration of assessment tools b. Participant recruitment b. Baseline data collection c. Clean data d. Preliminary data analysis
Q3 January-March 2026	
 a. Continued data collection b. Follow up assessment c. Enter and clean data d. Data analysis e. Prepare manuscripts
Q4 April-June 2026	
 a. Data analysis b. Prepare manuscripts and the final report c. Present findings

	Year 1											
Activity	Q1			Q2			Q3			Q4		
Recruitment Screening and recruitment												
Data Collection Baseline and follow up data collection												
Data Analysis												
Draft and submit manuscripts												

Study Endpoints

The primary endpoint of this pilot study is to evaluate the effectiveness of different body composition measurement tools (aim 1) before and 6 months after metabolic surgery (MS), and the secondary endpoints are to study the aim 2 and 3.

Aim 1: Evaluate the Effectiveness of Different Body Composition Measurement Tools

Rationale: Traditional methods like BMI and waist circumference may not accurately reflect changes in body composition, especially in patients with severe obesity. Advanced tools can provide more precise data.

Approach:

Participants: Recruit patients with severe obesity (BMI \geq 40) scheduled for MS.

Body Composition Measurements: BMI, waist circumference, leg strength, skeletal muscle mass, fat mass, free fat mass, extracellular water (ECW) and total body water (TBW)

Measurement Tools: Use the Bioelectrical Impedance Analysis (BIA), 3-compartment (3C) model optical imaging, isotope dilution, densitometry (BOD POD), Dual energy X-ray Absorptiometry (DXA), and MRI scan

Data Collection: Measure body composition using traditional and advanced measurement tools at baseline (pre-surgery) and 6 months post-surgery.

Analysis: Compare the effectiveness of each tool in assessing body composition changes.

Expected Outcome: Advanced tools will provide more accurate and clinically relevant data compared to traditional methods. We will use DXA as the reference standard and compare other methods against it.

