Aim 2: Assess Changes in Body Composition and Muscle Strength Following MS

Rationale: Understanding changes in body composition and muscle strength post-surgery can help improve patient outcomes and tailor post-operative care.

Approach:

Participants: Same cohort as Aim 1.

Measurements: Same cohort as Aim 1

Data Collection: Measure at baseline and 6 months post-surgery.

Analysis: Compare pre- and post-surgery data to evaluate changes in muscle strength and body composition.

Expected Outcome: Patients will experience a reduction in muscle strength, along with a more significant decrease in fat mass compared to muscle mass.

Aim 3: Compare Body Composition Changes Between SG and RYGB Patients

Rationale: Each metabolic surgery procedure may result in varying body composition outcomes. Comparing these can inform surgical decisions and patient counseling.

Approach:

[figure not shown]
Participants: Divide the cohort into two groups based on the type of surgery (SG or RYGB). Each group has 10 participants (5 male and 5 female)

Measurements: Use the same body composition tools as in Aim 1.

Data Collection: Measure at baseline and 6 months post-surgery.

Analysis: Compare body composition changes between the two groups.

Expected Outcome: RYGB patients will experience a greater reduction in subcutaneous, visceral, and total fat compared to SG patients after 6 months

Schematic of Non-Randomized Clinical Trial and Project Aims for BCOMS

Procedures Involved

Details of the procedures for this pilot study are:

Urine Collection (5 minutes): All participants will provide a urine sample to test for urine specific gravity. In addition, a urine pregnancy test will be administered for female participants that are pre and perimenopausal. A negative pregnancy result is required prior to proceeding with the following measurements.

Manual Anthropometry (20 minutes): Weight and height will be measured twice. Circumferences of waist, hip, midarm and midhigh (left and right) will be measured three times and recorded.

Blood draws (15 minutes): Phlebotomist collect blood samples at baseline and again at 4 hours. During the visit, a phlebotomist will complete two blood draws. The blood samples will be completed at the beginning of the visit. Blood samples (3ml) used for the sodium bromide and deuterium at baseline and 4hrs post-dose.

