Questionnaires (20 minutes): Participants will complete a questionnaire about their physical activity (attached) and diet (<https://asa24.nih.gov/>).

Participants will also complete 3 brief questionnaires that assess eating behaviors⁸⁻¹¹ (attached).

Abdomen, Pelvis and Thigh MRI scan (40 minutes): This scan will estimate the amount of skeletal muscle and regional (visceral) fat in the body. Participants will be required to remove all metal-containing objects from the body. Participants will be provided with earplugs and/or a headset to put over their ears for the duration of the scan. Participants will be given a call button if they need to notify the MRI tech during the scan. Participants will lie on their backs on the scanner table. The scan will start at the abdomen and proceed down to the thigh. The body will be scanned in sections. For the abdominal sections, participants will be asked to try their best to hold their breath a few times for approximately 15 seconds each time. Each participant will complete one scan.

Statistical Methods

Many of the comparisons will be exploratory and will need to be confirmed by follow-up studies. Continuous variables will be descriptively summarized by sample size, mean, standard deviation (SD), and standard error of the mean (SE). Type-II errors, i.e., failing to detect a significant effect when they exist, is important to this study. All tests of significance for comparisons will be performed at an alpha of 0.05. To address the goals outlined in the Aim, parametric statistical modeling, including analysis of covariance, multiple regression method and correlation analysis, will be employed where feasible. Paired testing will be used as well given the repeated measures design.

Data and Specimen Management

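### Aim 2 sets fat loss against muscle loss, but its stated analysis is a pre-post comparison that names neither that contrast nor its scale or tool

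*Protocol*

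**What the plan says.** The Objectives section hypothesises for Aim 2 a loss of muscle strength six months after surgery, "along with a more significant decrease in fat mass compared to muscle mass". The Aim 2 part of Study Endpoints repeats this as the expected outcome: "Patients will experience a reduction in muscle strength, along with a more significant decrease in fat mass compared to muscle mass". The analysis given there is: "Compare pre- and post-surgery data to evaluate changes in muscle strength and body composition".

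Statistical Methods is general and not tied to an aim. It says that "parametric statistical modeling, including analysis of covariance, multiple regression method and correlation analysis, will be employed where feasible", and adds: "Paired testing will be used as well given the repeated measures design". On the significance level it says: "All tests of significance for comparisons will be performed at an alpha of 0.05". On size, under Number of Subjects: "The pilot study will recruit 20 participants with severe obesity undergoing MS".

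For its measurements Aim 2 points back to Aim 1, which lists skeletal muscle mass and fat-free mass as separate quantities. Under Procedures Involved, DXA and BIA are each said to measure muscle and MRI to estimate skeletal muscle. Aim 2 does not say which of these supplies muscle mass.

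**The concern.** The hypothesis compares two changes within a person: the fall in fat and the fall in muscle. The stated analysis compares before with after, which gives one result per measure. Two such results placed side by side do not test whether one change exceeds the other.

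The phrase *more significant* also has no scale. It could mean a smaller p-value, more kilograms, a larger percentage of baseline, or a larger share of the weight lost. These readings can disagree on the same data. If the choice is left until the results are in, the answer to this half of Aim 2 depends on that choice. The stated purpose of Aim 2 is to help tailor care after surgery, and for that purpose disproportionate muscle loss needs to be told apart from loss that merely follows body size.

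**Working it through.** The protocol gives no effect size, SD or power for Aim 2, so there is no figure to reproduce. The check is a simulation.

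**Inputs from the protocol:** n = 20; alpha 0.05 (sidedness is not stated; two-sided assumed).

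**Assumptions, none from the documents:** baseline coefficient of variation 15%; SD of the proportional loss 7 percentage points; fat-muscle correlation 0.5 for both baseline and proportional loss; all 20 complete both visits. Baseline masses and mean losses are varied below. Each setting uses 20,000 simulated trials.

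**Analyses compared**, with F and M for fat and muscle, 0 for baseline, and dF and dM for the kilograms lost:
- (a) separate paired t-tests of dF and of dM;
- (b) paired t-test of dF − dM, the kilogram contrast;
- (c) paired t-test of dF/F0 − dM/M0, the proportional contrast.

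**Step 1: separate tests, equal 20% losses, 65 kg fat and 30 kg muscle.** Mean losses are 0.20 × 65 = 13.0 kg and 0.20 × 30 = 6.0 kg. The SD of a loss is about baseline × √(0.07² + (0.15 × 0.20)² + (0.15 × 0.07)²) = baseline × 0.077. The baseline therefore cancels from the t statistic, which is about (0.20/0.077) × √20 = 11.6 for both compartments. In the simulation both tests are significant in 100% of trials, and fat has the smaller p-value in 49.8%. Ranking the two p-values is a coin toss here.

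**Step 2: contrasts, equal 20% losses.** The expected kilogram contrast is 0.20 × (F0 − M0).

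| Baseline fat / muscle (kg) | Ratio | Expected dF − dM (kg) | (b) declares fat loss greater | (c) rejects, two-sided |
|---|---|---|---|---|
| 30 / 30 | 1.0 | 0 | 2.7% | 5.1% |
| 36 / 30 | 1.2 | 1.2 | 50.4% | 5.0% |
| 45 / 30 | 1.5 | 3.0 | 98.8% | 5.2% |
| 60 / 30 | 2.0 | 6.0 | 100% | 4.8% |
| 65 / 30 | 2.17 | 7.0 | 100% | 4.9% |
| 65 / 65 | 1.0 | 0 | 2.4% | 5.1% |
| 60 / 75 | 0.8 | −3.0 | 0% (muscle greater: 67.5%) | 4.8% |

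The last two rows stand for muscle read as a lean mass equal to or above fat mass. The 2.4% and 2.7% are close to the 2.5% expected by chance in one direction.

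**Step 3: muscle loses proportionally more.** With 65 kg fat falling 10% and 30 kg muscle falling 20%, mean losses are 6.5 and 6.0 kg. The kilogram contrast declares fat greater in 7.2% of trials and muscle greater in 0.7%, so it sees almost nothing. The proportional contrast rejects in 100%, with 0% in the direction of fat.

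**Step 4: can 20 participants support contrast (c)?** A paired test has 80% power at a standardised difference of 0.66. Under the assumptions the SD of the within-person difference is √(7² + 7² − 2 × 0.5 × 7 × 7) = 7 points, so the detectable difference is 0.66 × 7 = 4.6 percentage points. With assumed losses of 35% fat and 15% muscle, power is about 100%.

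**Log-ratio form.** A second simulation (fat 65 ± 12 kg, muscle 32 ± 5 kg, both falling 20% with SD 6 points) gave 5.05% rejections for the log-ratio contrast and more than 99.9% in favour of fat for the kilogram contrast.

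**The case against.** The case against has real weight. The Aim 2 line is a summary. Statistical Methods allows paired testing, and a paired test of fat change against muscle change fits that wording. Nowhere does the protocol say that two p-values will be compared. The exact contrast and its scale are often left to an analysis plan, which may exist and is not shown. The kilogram question is also legitimate: whether more of the lost weight is fat than muscle is an absolute question, and a significant result at 13 kg against 6 kg answers it correctly. Finally, Aim 2 is secondary, the study is a 20-person pilot, and the protocol calls many of its comparisons exploratory.

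Much of this stands, and it rules out three stronger readings that a reader might infer:

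- *The plan cannot test the hypothesis.* The data to be collected support a test, and the planned paired testing could supply it.
- *Aim 2 would be confirmed whatever the quality of the weight loss.* This fails even in kilograms: 10% of 65 kg fat is 6.5 kg, while 25% of 32 kg muscle is 8.0 kg, so the contrast points the other way.
- *A kilogram comparison favours fat automatically at a BMI of 40 or more.* The documents give no baseline composition. The effect needs fat to exceed muscle clearly, and it vanishes or reverses if muscle means lean mass of equal or larger size.

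The mismatch itself survives. The protocol sets the hypothesis and leaves its meaning open, and the analysis line written for it describes something else. An analysis plan could supply a test, but would first have to decide what is being claimed. The exploratory label does not settle that.

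**Conclusion.** The point holds as a mismatch between hypothesis and stated analysis, not as proof of an invalid test. Followed as written, the Aim 2 line yields separate pre-post results that do not address the fat-versus-muscle claim. The strength half of Aim 2 is a plain pre-post question and is unaffected.

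The size of the problem is conditional. Under equal proportional loss, the chance that a kilogram contrast declares fat loss greater runs from chance level to near certainty over baseline fat-to-muscle ratios of 1.0 to 1.5, while the proportional contrast stays near its nominal 5%. All of these figures rest on assumed baselines, spread and correlation. They show that the conclusion turns on a scale and a tool that the protocol does not fix; they do not predict this trial's result. The preference for a proportional scale is partly a matter of judgement. The need to choose one in advance is not.

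**What to change.** In the Aim 2 analysis line, name one contrast per participant, for example

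log(fat at 6 months / fat at baseline) − log(muscle at 6 months / muscle at baseline),

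from one named tool and one named muscle compartment. Test it once with a paired test and report it with a 95% confidence interval. Beside it, report the absolute changes in kilograms and lean loss as a share of weight lost, so that the absolute question is answered too. Reword the hypothesis in Objectives and in Study Endpoints so that *more significant* becomes a statement on that scale.

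The cost is a wording change, using measurements already scheduled at both visits. The small downside is that the conclusion is then tied to a scale and tool chosen in advance.

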Bioimpedance Analysis (BIA)	X	X
Abdomen, Pelvis and Thigh MRI	X	X

Pre-visit requirements:

Participants will fast at least 8 hours prior to their study. Participants will not exercise, shower, or use steam rooms or saunas at least two hours before evaluation.

Participants will bring their own form-fitting clothing attire that does not have metal- containing objects, like zippers, buttons, etc. We can provide clean linen for those that do not have form-fitting clothing attire. Patients will be asked to refrain from ingesting any dyes, calcium or barium supplements as this may affect DXA results.

In-person Measurements:

Each procedure and the measurement tool are listed down in sequence. A summary of the in-person measurements is described in table 1. The following body composition procedures will take place at the outpatient clinic (Clinical Trials Unit Core) at PBRC.

Table 1: In-person study measurements breakdown			
Sequence	Procedure	Time	Total time
Arrive at PBRC	Consenting Process	20m	20m
Outpatient Clinic	Vital signs; Fasting blood work, Urine testing (pregnancy test in women of childbearing age)	30m	50m
Baseline Measurements	Body Weight/Height	10m	1h
Isotopes	Drink Deuterium then Bromide dilutions.	10m	1h10m
Questionnaires	Complete diet and physical activity questionnaires	20m	1h30m
Dual-Energy X-ray Absorptiometry (DXA)	Measure body composition	20m	1h50m
BodPod	Measure body volume	20m	2h10m
3D Optical imaging	Automatically measure body dimensions with several devices	30m	2h40m
Anthropometrics	Waist Circumferences with tape measure	20m	3h
Six-minute Walk	Measure distance to complete 6 minutes of walking	20m	3h 20m
Muscle Strength & Endurance measure	Measure leg strength and endurance	30m	3h 50m
Outpatient Clinic	Blood samples follow up (collected at 4h post- dose)	20m	4h10m
Bioimpedance Analysis (BIA)	Measure body composition with several devices	20m	4h30m
Abdomen, Pelvis and Thigh MRI	Measure skeletal muscle, visceral and subcutaneous fats	40m	5h10m
Complete Study Measurement			

Study Timelines

The duration anticipated to enroll and complete data collection is 8 months after the IRB has been approved. These milestones will help ensure that this pilot study stays on track and achieves its objectives within the 1-year grant period.

Study Timeline (1-year)

Study Quarterly	Milestones

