This research does not involve individuals who are vulnerable to coercion or undue influence. We will seek consent only under circumstances that provide the prospective participant with an adequate opportunity to consider whether or not to participate. Once enrolled, a participant can voluntarily withdraw at any time point during the study.

Setting and Resource Available

Selection of study site: The study will be conducted at the Metamor Institute and PBRC which has a proven record of recruiting and treating patients with severe obesity. In 2023, the Metamor Institute had 1215 bariatric surgery outpatient clinic visits and performed 420 surgeries.

Experience in metabolic surgery in patients with severe obesity.

[name] is a pioneer of metabolic surgery (MS), has refined the techniques and approaches for patients with severe obesity.

In 2023, the total number of sleeve gastrectomy and gastric bypass procedures performed at Metamor were 201 and 117 cases, respectively. Majority (70%) of these patients have severe obesity (BMI \geq 40) and more than 70% were female.

Metamor Clinic (Jan-Dec 2023)	
Total Number of Outpatient visits	
Obesity Medicine	5000
Bariatric Surgery	1215
Dietitian	2520
Clinical Psychologist	1680
ANNUAL TOTAL	10 415 patients

2023 Metabolic Surgery Volumes

OLOL RMC	Total Volume	Sleeve Gastrectomy	Gastric Bypass	Duodenal switch/ SADI	Revisions/ Conversions
Total Cases	420	201	117	5	72

This pilot study leverages the expertise at the Metamor Institute, the Metabolism and Body Composition Laboratory and the Biomedical Imaging Center, at PBRC. By integrating knowledge from metabolic surgery, metabolism, advanced imaging, we aim to develop an innovative approach to assessing body composition outcomes in metabolic surgery patients. This collaboration will enhance the robustness and applicability of our findings. With state-of-the-art facilities and robust institutional support, PBRC provides the ideal environment to achieve our research goals. Our well-structured and highly skilled team collaboration is uniquely equipped to conduct this pilot research and deliver meaningful outcomes.

Metamor census: Metabolic Surgery (Jan-September 2023)							
Total Patients	BMI \geq 40	Female	Male	African American	White	Asian	Others
306	216	192	24	125	89	1	1

Prior Approvals

There is no prior approval.

Data Collection, Storage and Confidentiality

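### Aim 3 states 5 men and 5 women per procedure, but the protocol's own census and timeline are unlikely to deliver them, so the sex balance cannot be relied on

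*Protocol*

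**What the plan says.** Protocol, Study Endpoints, Aim 3 divides the cohort by type of operation and says: "Each group has 10 participants (5 male and 5 female". This agrees with the total under Number of Subjects: "The pilot study will recruit 20 participants with severe obesity undergoing MS". The Aim 3 analysis line reads: "Analysis: Compare body composition changes between the two groups". Statistical Methods adds that analysis of covariance and multiple regression will be used where possible, without naming covariates.

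Setting and Resource Available gives the source population. The table titled "Metamor census: Metabolic Surgery (Jan-September 2023" has the row "306 216 192 24 125 89 1 1": 306 patients, 216 with BMI of at least 40, of whom 192 were women and 24 men. For the whole of 2023, "the total number of sleeve gastrectomy and gastric bypass procedures performed at Metamor were 201 and 117 cases, respectively", out of a total volume of 420.

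Study Timelines says: "The duration anticipated to enroll and complete data collection is 8 months after the IRB has been approved". Duration of Study Participation places the second visit 6 months after surgery. The quarterly table lists recruitment in Q1 and Q2. The eligibility criteria admit either sex, and Recruitment Methods contains no sex stratum, cap or order of enrolment.

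**The concern.** The 5/5 split is written as a fixed feature of the design, not as a hope. It asks for a cohort that is 50% male from a clinic population that is 11% male, in a short window, with RYGB men as the scarcest stratum. Nothing in the recruitment text says how this would be achieved.

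Two things depend on it. First, the Background faults the earlier gastric bypass study for including only women; a mostly female cohort would largely repeat that limitation. Second, SG and RYGB are not randomised, and the equal sex split is the only balancing device the protocol describes for comparing them. If the split does not materialise, a reader can no longer assume that the two groups are alike in sex.

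**Working it through.** **The plan's own figures.** 2 procedures x (5 + 5) = 20, which matches the stated total. 192 + 24 = 216, and 216/306 = 70.6%, which matches the 70% with BMI of at least 40 given in the text. No sample size calculation is offered, so there is none to reproduce.

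**Inputs.**
- Men with BMI of at least 40: 24 in 9 months, so 24/9 = 2.67 a month; male share 24/216 = 11.1%.
- RYGB share: 117/(201 + 117) = 117/318 = 36.8% of the two eligible procedures, or 117/420 = 27.9% of all cases. SG share: 201/318 = 63.2% or 201/420 = 47.9%. The ranges below run between these denominators. (The listed procedure columns sum to 395, which gives values in between.)
- Enrolment window: 8 - 6 = 2 months at most, because the 6 months run from surgery, not from the first visit. All of Q1-Q2 gives 6 months.
- Uptake among eligible men is not stated. It is assumed here, from 30% to 100%.
- Men are assumed to have the same procedure mix as all patients, and 2023 rates to persist.

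**Formula.** Expected men in a group = 2.67 x months x procedure share x uptake. The chance of meeting the quota is P(SG men >= 5) x P(RYGB men >= 5), each count Poisson with that mean. For example, 2 months at full uptake with the 318 denominator: 5.33 x 0.632 = 3.37 SG men and 5.33 x 0.368 = 1.96 RYGB men; the product of the two tail probabilities is 0.0124.

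| Window | Men (all procedures) | SG men | RYGB men | P(5 + 5), 100% uptake | 50% uptake | 30% uptake |
|---|---|---|---|---|---|---|
| 2 months | 5.3 | 2.6-3.4 | 1.5-2.0 | 0.2%-1.2% | about 0.01% or less | about 0 |
| 6 months | 16 | 7.7-10.1 | 4.5-5.9 | 40%-68% | 3%-10% | under 1% |
| 9 months | 24 | 11.5-15.2 | 6.7-8.8 | 79%-94% | 17%-39% | 1%-6% |

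The expected counts are at full uptake. To expect 5 RYGB men, the uptake needed among them is 5/5.9 to 5/4.5, or 85%-112%, over 6 months, and 57%-75% over 9 months. The 440 lb limit and the metal and implant exclusions lower all these figures. The 6-month window is itself generous, since Q1 also contains protocol completion and ethics approval.

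**If enrolment simply follows the census.** Expected men = 20 x 0.111 = 2.2. The exact binomial chance of 5 or more men in a group of 10 is 0.26%.

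**Balance between the groups.** If both procedures share the 11.1% male fraction and enrolment is unselected, the number of men differs between two groups of 10 by 0 or 1 with probability 73%, by 2 or more with 27%, and by 3 or more with 7%.

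**The case against.** The strongest reply is that 24 men in 9 months exceeds the 10 required, so the census alone does not rule the quota out. That stands. The difficulty arises only when the census is combined with the RYGB share and the enrolment window. The 2-month window is derived, not stated; the 8 months are described as anticipated; and the quarterly table allows recruitment over two quarters. On that reading, a study that actively seeks men has a 40%-68% chance if every eligible man agrees. This version is also dated after the planned recruitment quarters, and the document does not say who had been enrolled by then. A reader might infer that the stated groups cannot exist; the document supports unlikely, not impossible.

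A reader might also infer that sex will be confounded with procedure. That needs the male share to differ between SG and RYGB, and the protocol gives no sex-by-procedure counts. A shortage of men in both groups would usually leave two mostly female groups of similar mix. Nor can a bias in kilograms be quoted, because the document gives no sex difference in fat loss.

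Finally, a reader might infer that the comparison is unadjusted. Statistical Methods already names analysis of covariance, and the covariate list may sit in an analysis plan that is not at hand. Its absence here is not counted as an error. The same section also calls many comparisons exploratory.

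None of this reconciles the 5/5 statement with the census and the 8-month total, or supplies a recruitment rule that would produce it.

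**Conclusion.** The concern holds as an inconsistency between a stated group composition and the protocol's own figures. Within the 8-month total, about 5.3 men are expected where 10 are needed. Even on the more generous two-quarter calendar, success is unlikely (3%-10%) unless uptake is well above 50%. RYGB men are the binding stratum.

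The firmer consequence is a mostly female cohort. The second is that sex balance between SG and RYGB cannot be taken as given, although imbalance is a possibility and not a forecast: a difference of 2 or more men has a probability of about 27% under a common male share.

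These figures rest on 2023 rates persisting, men following the overall procedure mix, no dropout and assumed uptake. Aim 3 is a secondary aim of a pilot, and the primary comparison of measurement tools does not depend on sex balance between procedures. The point is worth correcting but does not threaten the study as a whole.

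**What to change.** Reconcile the Aim 3 group statement with the census, the visit schedule and the timeline, in one of two ways:

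- State the target as 10 SG and 10 RYGB, with men enrolled preferentially as they become available, and give the number of men realistically expected.
- Keep a sex target, but add a sex-stratified enrolment rule and an enrolment window that can meet it.

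Within the analysis of covariance that Statistical Methods already names, specify Aim 3 as the 6-month value regressed on procedure and the baseline value of the same measure, with sex added where both groups include men. The condition matters: at the census mix a group of 10 has no men with probability 0.889^10 = 31%, and a sex term would then rest on extrapolation. Report the adjusted difference with a 95% confidence interval and describe it as associational.

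The first option costs fewer men than the protocol now states; the second costs time. The analysis change costs one or two degrees of freedom (17 or 16 residual, against 18 for a plain two-group comparison of 20) and needs no new data, since baseline values and sex are already available.
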